### 7.2.1 Exploratory Analysis for Immunogenicity

To evaluate the possible impact of imbalance in sex and age on the immunogenicity endpoints, exploratory analyses will be conducted using linear regression to compare the immunogenicity response at Day 37 between each AV7909 + antibiotic group and the AV7909 only group, i.e., between Group 1 (AV7909 + ciprofloxacin) and Group 3 (AV7909) and between Group 2 (AV7909 + doxycycline) and Group 3 (AV7909). In the linear regression models, the stratification factor, study site, will be included in the model as a random effect; treatment group, participant sex and age will be included as fixed factors with age being dichotomized into ≤30 years and >30 years. The adjusted GMT ratio for TNA NF50 will be provided with 95% confidence interval. Any differences between the exploratory (adjusted) and the primary (unadjusted) analyses will be discussed in the final CSR.

## 8 SAFETY ANALYSIS

All safety data will be presented in the form of tabulations and listings, based on the Safety Population. Data summaries will be tabulated by treatment group as specified in [Section 3.2](#).

### 8.1 Adverse Events

AEs will be coded to system organ class (SOC) and preferred term (PT) according to the Medical Dictionary for Regulatory Activities (MedDRA). A subject data listing of all AEs (including treatment-emergent AEs (TEAEs) and non-TEAEs) sorted by treatment group, subject ID and AE start date/time will be provided based on the Safety Population. This listing

will include a “non-treatment-emergent” flag and the date of the last IP dose. Only TEAEs will be included in the AE summaries described below.

### 8.1.1 Overall Summary of TEAEs

A treatment emergent adverse event (TEAE) is defined as an AE that presents after the initiation of treatment or any AEs already present that worsen in either intensity or frequency following treatment. For programming purpose, any AEs with start date on or after the date of first exposure of any study treatment will be counted as treatment emergent. AEs with missing start dates, but with stop dates overlapping into the treatment period will also be counted as treatment emergent.

An overall summary of the following TEAE categories will be provided:

- TEAEs
- TEAEs related to any study treatment
- Grade 3/4 TEAEs
- Grade 3/4 TEAEs related to any study treatment
- Serious TEAEs
- Serious TEAEs related to any study treatment
- TEAEs leading to death
- TEAEs leading to discontinuation of any study treatment
- TEAEs leading to study withdrawal
- AESIs
- AESIs related to study vaccine

### 8.1.2 All TEAEs

All TEAEs will be tabulated by SOC and PT (in descending order of participant incidence in “AV7909 Total” column).

TEAEs with 5% or more for a PT term in any treatment group will be tabulated by SOC and PT.

All TEAEs will be summarized by SOC, PT, severity, and treatment group. The severity of AEs will be assessed by the PI or designee using toxicity grading (Grade 1 to 4) according to Protocol EBS.AVA.210, [Appendix A](#). All TEAEs will also be summarized by SOC, PT, relationship to study treatment, and treatment group. Participants having the same TEAE more than once will be counted once for each PT and once within each SOC at the maximum severity and relatedness. If the severity/relatedness is missing for one or more of the occurrences, the maximum severity/relatedness of the remaining occurrences will be used.

TEAE summaries will be provided for TEAEs through the Final Study Visit (Day 51) and for all TEAEs through the 12-month follow up , respectively.

### 8.1.3 Drug/Vaccine Related TEAEs

Adverse event causal relationship to the study treatment will be assessed by the PI or designee using terms and scales “Unrelated”, “Possibly related”, “Probably related”, and “Definitely related”. If the relationship between the AE and the study treatment is determined to be “Possibly” or “Probably” or “Definitely related”, the event will be considered as related to the IP.

To assess the causality between AEs and the study treatment ciprofloxacin, doxycycline, and AV7909, TEAEs will be tabulated with the structures as follows:

- TEAEs by SOC, PT, and Relationship to Study Vaccine.
- TEAEs by SOC, PT, and Relationship to Antibiotics.
- TEAEs onset prior to the first vaccination by SOC, PT, and relationship to ciprofloxacin or Doxycycline.

### 8.1.4 Serious TEAEs

Serious TEAEs will be tabulated using the MedDRA coded terms of SOC and PT by relationship to study treatment (ciprofloxacin, doxycycline, AV7909). A subject data listing of all serious TEAEs will be provided.

### 8.1.5 Adverse Events of Special Interest (AESI)

Treatment-emergent AESIs determined to be of autoimmune etiology based on decision of the DSMB will be tabulated by SOC, PT, and relationship with AV7909. A subject data listing of all AESIs will be provided.

### 8.1.6 TEAEs Leading to Discontinuation of Study Treatment, and Study Withdrawal

Separate tabulations will be displayed for TEAEs leading to discontinuation of antibiotic or vaccination, and withdrawal from the study.

### 8.1.7 Deaths

A large number of deaths is not expected in this study with healthy participants. A tabulation and subject data listing of all deaths will be provided as appropriate.

## 8.2 Clinical Laboratory Tests

Clinical laboratory results for the lab analytes that appear in Protocol EBS.AVA.210, [Table 13](#) will be assigned by the central laboratory a toxicity grade (Grade 1=mild through Grade 4=potentially life-threatening).

Central laboratory measurements will be tabulated by treatment group as follows:

- Observed values and changes from baseline of continuous laboratory variables (hematology, serum chemistry, and selected urinalysis parameters [e.g., specific

gravity]) will be summarized using descriptive statistics (n, mean, SD, median, minimum, and maximum) by study visit and treatment group.

- Observed values of categorical laboratory analytes (e.g., urinary protein) and shifts from baseline (number and percentage) will be summarized by study visit and treatment group.
- Shift from baseline according to normal reference ranges (reported as ‘Low’, ‘Normal’, and ‘High’) will be summarized (number and percentage) by study visit and treatment group.
- Shift from baseline according to toxicity grading criteria grade (Grade 0, Grade 1-4) will be summarized (number and percentages) by study visit for analytes that appear in Protocol EBS.AVA.210, **Table 13**. Grade 0 includes all values within normal range or value not meeting criteria for toxicity of at least Grade 1.
- Frequency and percentage of participants with the highest grade of post baseline abnormal laboratory values according to toxicity grading criteria grade (Grade 1-4).
- Post baseline abnormal laboratory results with Grade 3 or higher

All laboratory records will be provided in the subject data listings. This listing will include all test results that are collected throughout the study for the analyte of interest, with all applicable severity grades or abnormal flags displayed.

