Investigational sites will be automatically notified of any Grade 3 or higher laboratory abnormalities. For any Grade 3 or higher laboratory result, the test will be repeated as soon as possible by the central lab using the same blood sample to confirm the result. The PI or designee must request the participant return to the clinic for an unscheduled visit for an assessment of clinical status. The decision to redraw laboratory tests will be made by the PI (with notification to the MM) and/or MM and will be based on the type and severity of the laboratory abnormality and the clinical status of the participant. Any Grade 3 or higher neutropenia or lymphopenia must be evaluated with an unscheduled repeat complete blood count (CBC) approximately 72 hours after the initial specimen was drawn.

If the original (retested sample) or repeat laboratory value is Grade 3 or higher or determined by the PI to be a clinically significant change from baseline for that participant, this will be considered an AE and will be recorded on the AE eCRF. Any other clinical laboratory abnormalities must also be reported as AEs if considered by the PI to be a clinically significant change from baseline. If an abnormal laboratory test result is a sign of a disease or syndrome, the disease or syndrome will be recorded as the AE/SAE and not the abnormal laboratory result. Clinical laboratory abnormalities may trigger individual participant or study halting rules (see [Section 7.1](#) and [Section 7.3](#)) and may require discontinuation of treatment.

Table 10: Screening/Safety Clinical Laboratory Tests

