10.6.2. Clinical Laboratory Data

Safety clinical laboratory results will be tabulated by visit and group and listed by individual participant. Observed values and changes from baseline of continuous laboratory variables (hematology, serum chemistry, and selected urinalysis parameters [eg, specific gravity]) will be summarized using descriptive statistics (n, mean, median, SD, minimum, and maximum). Observed values of categorical laboratory variables (eg, urinary protein), incidences of abnormalities by analyte according to laboratory normal ranges and highest toxicity grade (refer to [Table 13 in Appendix A](#)), and shifts from baseline will be summarized descriptively (number and percentage) by visit and treatment group. Shift tables will be produced to reflect shifts from baseline values against the lab normal ranges (low, normal, high) as well as against toxicity grading criteria (Grade 0, Grade 1, Grade 2, Grade 3, Grade 4). Note: Grade 0 = laboratory value within normal range or laboratory value does not meet criteria for toxicity of at least Grade 1

AV7909 Anthrax Vaccine

IND 014451

Protocol EBS.AVA.210, Version 3.0 (28 October 2019)

(refer to [Table 13](#) in [Appendix A](#)). Screening (serology, urine drug screen, FSH) and pregnancy test results will be listed by individual participant.

In tabulations, the last measurement before the first IP administration will be used as the baseline value. In listings, laboratory values outside of the reference range will be flagged: L=low compared to the lower limit of the normal range, H=high compared to the upper limit of the normal range. Additionally, laboratory abnormalities associated with a severity grade based on the toxicity grading criteria (refer to [Table 13](#) in [Appendix A](#)) will be flagged: Grade 1 = Mild, Grade 2 = moderate, Grade 3 = severe, and Grade 4 = potentially life-threatening. Grade 3 or higher laboratory abnormalities will be summarized in a separate listing.

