Bilirubin (when accompanied by any increase in Liver Function Test) increase by factor	1.1–1.25 x ULN	1.26–1.5 x ULN	1.51–1.75 x ULN	> 1.75 x ULN
Bilirubin (when Liver Function Test is normal) increase by factor	1.1–1.5 x ULN	1.6–2.0 x ULN	2.0–3.0 x ULN	> 3.0 x ULN
Hematology				
Hemoglobin, female (g/dL)	11.0–12.0	9.5–10.9	8.0–9.4	<8.0
Hemoglobin decrease from baseline value, female (g/dL)	Any decrease–1.5	1.6–2.0	2.1–5.0	>5.0
Hemoglobin, male (g/dL)	12.5–13.5	10.5–12.4	8.5–10.4	<8.5
Hemoglobin decrease from baseline value, male (g/dL)	Any decrease–1.5	1.6–2.0	2.1–5.0	>5.0

AV7909 Anthrax Vaccine

IND 014451

Protocol EBS.AVA.210, Version 3.0 (28 October 2019)

Panel and Analyte^a	Mild (Grade 1)	Moderate (Grade 2)	Severe (Grade 3)	Potentially Life Threatening (Grade 4)^b
WBC increase (cell/mm ³)	10,800–15,000	15,001–20,000	20,001–25,000	>25,000
WBC decrease (cell/mm ³)	2,500–3,500	1,500–2,499	1,000–1,499	<1,000
Lymphocyte decrease (cell/mm ³)	750–1,000	500–749	250–499	<250
Neutrophil decrease (cell/mm ³)	1,500–2,000	1,000–1,499	500–999	<500
Eosinophils (cell/mm ³)	650–1,500	1,501–5,000	>5,000	Hypereosinophilic
Platelets decrease (cell/mm ³)	125,000–140,000	100,000–124,000	25,000–99,000	<25,000
Urine				
Protein	Trace	1+	2+	Hospitalization or dialysis
Glucose	Trace	1+	2+	Hospitalization for hyperglycemia
Blood (microscopic) (RBC/hpf)	1–10	11–50	>50 and/or gross blood	Hospitalization or PRBC transfusion

ALT = alanine aminotransferase; AST = aspartate aminotransferase; HPF = high power field; PRBC = packed red blood cells; RBC = red blood cells; ULN = upper limit of normal range; WBC = white blood cell.

^a Laboratory normal reference ranges have not been taken into consideration for the toxicity grading scale.

^b The clinical signs or symptoms associated with laboratory abnormalities might result in characterization of the laboratory abnormalities as Potentially Life Threatening (Grade 4). For example, a low sodium value that falls within a Grade 3 parameter (125-129 mE/L) will be recorded as a Grade 4 hyponatremia event if the participant had a new seizure associated with the low sodium value.

AV7909 Anthrax Vaccine

IND 014451

Protocol EBS.AVA.210, Version 3.0 (28 October 2019)

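### An in-range hemoglobin fall can be a Grade 3 adverse event and still be Grade 0 in the laboratory toxicity shift table

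*SAP*

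**What the plan says.** SAP 8.2 plans a table by visit for the analytes in protocol Table 13: "Shift from baseline according to toxicity grading criteria grade (Grade 0, Grade 1-4) will be summarized". It defines the lowest category for that table as follows: "Grade 0 includes all values within normal range or value not meeting criteria for toxicity of at least Grade 1". Protocol 10.6.2 has the same rule: "Grade 0 = laboratory value within normal range or laboratory value does not meet criteria for toxicity of at least Grade 1". In both places the two conditions are alternatives, so being in range is enough for Grade 0.

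Grades 1 to 4 come from protocol Appendix A, Table 13. Under SAP 8.2, results for those analytes "will be assigned by the central laboratory a toxicity grade". Footnote a to Table 13 reads: "Laboratory normal reference ranges have not been taken into consideration for the toxicity grading scale". For each sex, Table 13 has one hemoglobin row on the absolute value and one on the decrease from baseline. In the decrease rows Grade 1 is "Any decrease–1.5" g/dL, Grade 2 is 1.6–2.0, Grade 3 is 2.1–5.0 and Grade 4 is above 5.0.

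Protocol 8.3.2 ties adverse event reporting to the grade: "If the original (retested sample) or repeat laboratory value is Grade 3 or higher", it is recorded as an adverse event. Protocol 9.2.3 repeats this and exempts only results covered by a disease or syndrome already reported. Neither section exempts an in-range value.

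No rule says which definition prevails. SAP 8.3, on vital signs, defines Grade 0 only as failing to meet any Grade 1 criterion, with no normal-range alternative.

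**The concern.** A decrease criterion can be met while the value stays inside the reference range. For such a value the two rules give different grades, and nothing ranks them. The visible result would be a participant with a Grade 3 hemoglobin adverse event who appears in the shift table as Grade 0 at baseline and Grade 0 at Day 51. The milder and more frequent result is a Grade 1 column for hemoglobin whose count depends on how a programmer reads one sentence.

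The decrease rows are the clear case, but not the only possible one. If the central laboratory's lower limit lies inside a Table 13 band (for men, Grade 1 on the absolute row is 12.5–13.5 g/dL), the absolute row conflicts in the same way. The documents do not give the laboratory's limits.

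**Working it through.** The plan states no rate or count on this point, so there is no figure to reproduce. The contradiction follows from the text; only its size needs assumptions.

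**Single values.** Assume reference ranges of 13.5–17.5 g/dL (men) and 12.0–15.5 g/dL (women).

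| Baseline to Day 51 (g/dL) | Decrease | Table 13, absolute row | Table 13, decrease row | Shift-table rule |
|---|---|---|---|---|
| Man, 16.8 to 14.6 | 2.2 | no grade | Grade 3 | Grade 0 (in range) |
| Woman, 15.2 to 13.1 | 2.1 | no grade | Grade 3 | Grade 0 (in range) |
| Man, 15.0 to 14.9 | 0.1 | no grade | Grade 1 | Grade 0 (in range) |

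The Grade 3/Grade 0 pair does not depend on these limits. With both values in range it can arise under any reference range at least 2.1 g/dL wide.

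**Share with a Grade 1 decrease.** Safety laboratories are scheduled only at Screening and at Day 51 or early withdrawal (protocol 8.3.2), so each participant has one scheduled post-baseline value. Let the change be normal with mean μ (negative for a fall) and SD σ, reported to 0.1 g/dL. Then

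P(Grade 1 decrease) = Φ((1.55 + μ)/σ) − Φ((0.05 + μ)/σ).

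With μ = 0 this gives 0.450, 0.462, 0.449 and 0.419 for σ = 0.4, 0.6, 0.8 and 1.0 (assumed).

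**Share that switches.** A participant switches only if the Day 51 value is also in range. A simulation of 300,000 participants added that condition. It assumed half men, mean hemoglobin 15.3 g/dL (men) and 13.5 g/dL (women), between-person SD 1.0, and the ranges above. It took the higher of the two hemoglobin rows as the Table 13 grade.

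Percentage in range with Table 13 Grade 1:

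| Mean change (g/dL) | σ = 0.4 | 0.6 | 0.8 | 1.0 |
|---|---|---|---|---|
| +0.3 | 18.3 | 26.2 | 29.3 | 29.8 |
| 0 | 41.8 | 42.0 | 40.2 | 36.9 |
| −0.3 | 65.3 | 56.3 | 48.6 | 41.9 |
| −0.6 | 76.5 | 63.8 | 52.5 | 43.7 |
| −1.0 | 68.6 | 57.9 | 48.2 | 40.5 |

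With lower limits of 12.5 and 11.2 g/dL instead, μ = 0 and σ = 0.6, the share is 47%. Zero mean change therefore gives about 37–47%, and the whole grid about 18–77%.

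Expected number of 210 participants in range with Table 13 Grade 3:

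| Mean change (g/dL) | σ = 0.4 | 0.6 | 0.8 | 1.0 |
|---|---|---|---|---|
| 0 | 0.0 | 0.0 | 0.7 | 2.8 |
| −0.6 | 0.0 | 1.0 | 4.2 | 8.5 |
| −1.0 | 0.5 | 4.5 | 9.9 | 14.6 |

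A net fall deserves a place in the grid. Group 1A gives 4 × 14 + 10 = 66 PK and trough samples and Group 2A gives 4 × 14 + 14 = 70, while the other groups give none. Blood volumes are not stated, so any difference between groups is a possibility and not a forecast.

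**The case against.** The best case for leaving the text alone is that little depends on it. In SAP 8.2 the Grade 0 sentence belongs to the toxicity shift bullet only. The summaries of highest post-baseline grade and of Grade 3 or higher use Grades 1 to 4, which the central laboratory assigns. Change from baseline is summarized with minimum and maximum, and the listings show all grades and flags. Confirmed Grade 3 results appear as adverse events. No laboratory hypothesis is tested. All of this stands.

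It also rules out some stronger conclusions that a reader might draw:

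- That the secondary endpoint on laboratory abnormalities changes with the clause. The Grade 0 sentence does not govern the incidence bullets, and protocol 10.6.2 lists incidences and shifts separately.
- That the laboratory tables must contradict each other. The highest-grade and Grade 3+ bullets are limited to abnormal values. If abnormal means graded under Table 13, they disagree with the shift table; if it means out of range, in-range falls are missing from both. The text does not settle this.
- That in-range Grade 2 and 3 falls vanish from the report. They drop out of one table.

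A programmer could also apply only the second alternative, and then nobody switches. The text does not say to do so. Finally, one could keep the range screen and add a precedence sentence, which would spare many Grade 1 entries caused by ordinary variation. That would remove the ambiguity but leave the shift table at odds with the adverse event grade.

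**Conclusion.** The contradiction is in the documents and needs no outside figure: followed as written, the Grade 0 rule can classify a Grade 3 laboratory result, reportable as an adverse event once confirmed, as Grade 0. It affects the laboratory toxicity shift table and possibly that table's agreement with the highest-grade and Grade 3+ tables.

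Its size rests on assumed reference limits, variability and mean change. About 37–47% of participants would switch between Grade 0 and Grade 1 with zero mean change, and 18–77% over mean changes of +0.3 to −1.0 g/dL. A reader might be tempted to say flatly that half of participants switch. The documents support no such figure, and the share with any decrease at all is not the share that switches: decreases above 1.5 g/dL and out-of-range values have to be removed. The Grade 3/Grade 0 clash should be rare: about 0–3 of 210 with zero mean change and 0–9 with a mean fall of 0.6 g/dL. Only at the far end of the grid, a mean fall of 1.0 g/dL, does it reach 15. Severity is minor.

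**What to change.** In protocol 10.6.2 and SAP 8.2, delete the normal-range alternative so that Grade 0 means a value that meets no Table 13 Grade 1 to 4 criterion. That matches the vital-signs definition in SAP 8.3. Present absolute hemoglobin and hemoglobin decrease from baseline as two separate rows. It would also help to say in SAP 8.2 whether abnormal, in the highest-grade and Grade 3+ bullets, means graded under Table 13.

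The cost is a few words in each document. Nothing is lost on reference ranges, because SAP 8.2 already plans a separate low/normal/high shift table. The drawback is more Grade 1 entries in the hemoglobin-decrease row, many of them from ordinary variation; the separate row keeps them from obscuring the absolute values.

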5.2. Exclusion Criteria

Individuals meeting any of the following exclusion criteria will be excluded from study participation:

1. A Screening clinical laboratory test result greater than the central laboratory's upper limit of normal (ULN) for aspartate aminotransferase (AST), alanine aminotransferase (ALT), random glucose, total bilirubin, blood urea nitrogen (BUN), or creatinine. Other serum chemistry parameters that are not within the reference range will not be considered exclusionary unless deemed clinically significant by the principal investigator.
2. History of allergic reaction or intolerance to quinolone antimicrobials or any medical condition that would contraindicate the use of ciprofloxacin, including and not limited to vascular disorders, tendon disorders, certain genetic connective tissue disorders (eg, Marfan and Ehlers–Danlos syndrome), prolongation of QT interval, seizures, peripheral neuropathy, increased risk of *C. difficile* infection (see ciprofloxacin prescribing information in the Pharmacy Manual).
3. History of allergic reaction or intolerance to tetracycline antibiotics or any medical condition that would contraindicate the use of doxycycline including an increased risk of *C. difficile* infection, increases in BUN or an increased sensitivity to direct sunlight or ultraviolet radiation resulting in erythema (see doxycycline prescribing information in the Pharmacy Manual).
4. Has a need for any of the prohibited medications in [Section 6.5.1](#) or requires the medications/foods within the prohibited times in [Section 5.3.1.1](#).
5. Have a tattoo/scar/birthmark or any other skin condition affecting the deltoid area that may interfere with injection site assessments.
6. History of anthrax disease, suspected exposure to anthrax, or previous vaccination with any anthrax vaccine.
7. Have previously served in the military any time after 1990 or plan to enlist in the military any time from Screening through the final telephone contact.
8. Previous anaphylactic reaction, severe systemic response, or serious hypersensitivity to a prior immunization or a known allergy to synthetic ODNs, aluminum, formaldehyde, benzethonium chloride (phemerol).
9. Plan to have an elective surgery at any point during the study until after the final safety phone contact.
10. Have donated or plan to donate blood within one month prior to enrollment or at any point during the study until after the final safety phone contact.

AV7909 Anthrax Vaccine

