## 2.3.2 Secondary Endpoints

### 2.3.2.1 Secondary Safety Endpoints

- Incidences of AEs from the first dose of any IP through the Final Study Visit (Day 51)
- Incidences of serious AEs (SAEs) from the first dose of any IP until the 12-month follow-up (Day 388)
- Incidences of solicited systemic and injection site reactions reported in participant e-diaries following each vaccination
- Incidences of AESIs from the first dose of any IP until the 12-month follow-up (Day 388)
- Incidences of clinical laboratory abnormalities

No hypothesis testing is planned for any of the safety endpoints.

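### The laboratory incidence table ignores the baseline grade, and no planned laboratory summary is both baseline-referenced and complete for the worst post-baseline result

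*SAP*

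**What the plan says.** SAP 2.3.2.1 lists "Incidences of clinical laboratory abnormalities" among the secondary safety endpoints. Neither document says whether an incident abnormality must be new or worse than at entry. Protocol 10.6.2 plans "incidences of abnormalities by analyte according to laboratory normal ranges and highest toxicity grade" alongside shifts from baseline.

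SAP 8.2 turns the graded part into "Frequency and percentage of participants with the highest grade of post baseline abnormal laboratory values according to toxicity grading criteria grade (Grade 1-4", without mention of the baseline grade. The same section plans displays that do refer to baseline:

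- by toxicity grade: "Shift from baseline according to toxicity grading criteria grade (Grade 0, Grade 1-4) will be summarized (number and percentages) by study visit", for the analytes in Protocol Table 13;
- shifts by Low, Normal and High, and shifts for categorical analytes;
- "Observed values and changes from baseline of continuous laboratory variables (hematology, serum chemistry, and selected urinalysis parameters".

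SAP 3.4 keeps unscheduled results out of by-visit summaries and admits them to maximum-grade tables and listings. SAP Table 2 gives analysis windows for baseline and Days 1, 8, 23, 37 and 51 (Days 50 to 52), with no row for the early withdrawal visit. Protocol 8.3.2 schedules safety laboratories at Screening and at Day 51, or at early withdrawal if that comes first.

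For adverse events, SAP 8.1.1 does have a worsening rule. Besides new events it counts "any AEs already present that worsen in either intensity or frequency following treatment".

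**The concern.** An incidence is normally read as the share of participants in whom something new appeared. The highest-grade table does not measure that if participants can enter with a grade. A participant with the same Grade 1 neutrophil count at Screening and Day 51 would be counted exactly like one who moved from Grade 0 to Grade 1.

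Entry with a grade is possible. Protocol 5.2, criterion 1, bars values above the upper limit of normal for AST, ALT, random glucose, total bilirubin, BUN and creatinine. It continues: "Other serum chemistry parameters that are not within the reference range will not be considered exclusionary unless deemed clinically significant". No numeric limit applies to neutrophils, lymphocytes, white cells, platelets or eosinophils, to low glucose, or to urine protein or blood.

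At stake is what a reader can conclude about new laboratory abnormalities when antibiotic and vaccine are given together. Chance differences between groups at entry also pass straight into the table.

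**Working it through.** **Step 1. Where each kind of result appears.** This follows from reading SAP 8.2 with SAP 3.4 and Table 2.

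| Participant | Highest-grade table | Grade-shift table |
|---|---|---|
| Same grade at baseline and scheduled Day 51 | Counted | Shown as unchanged |
| New or worse grade at scheduled Day 51 | Counted | Shown as worsened |
| Worse grade only at an unscheduled draw | Counted | Absent |
| Worse grade only at early withdrawal before Day 50 | Counted, as a post-baseline result (inferred) | No laboratory visit to place it in |

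For the last row, a withdrawal sample that happens to fall on Day 8, 22 to 24 or 36 to 38 could be given one of those labels by date, although no safety laboratory is planned at those visits. On other days before Day 50 it has no label.

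So for scheduled Day 51 samples the shift table yields the new-or-worsened count by analyte. For the last two rows, no laboratory summary table compares the result with baseline.

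**Step 2. Illustration of the mixing.** The plan states no figure to reproduce and gives no baseline grade rates. The rates below are assumptions.

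Inputs: 70 participants per group (SAP 2.4); b = share with a grade at baseline; q = share of those still graded later; i = new-onset rate among the rest, taken as 5% against 15%. Further worsening among those already graded is ignored for simplicity.

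- Any post-baseline grade: p = b·q + (1 − b)·i
- Emergent grade: e = (1 − b)·i
- 95% half-width for the difference: 1.96 × √[p0(1 − p0)/70 + p1(1 − p1)/70], and likewise for e

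Example with b = 5% and q = 1: p0 = 0.05 + 0.95 × 0.05 = 9.75%; p1 = 0.05 + 0.95 × 0.15 = 19.25%; ratio 1.97; difference 9.5 points.

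| b (q = 1) | Any grade, % | Ratio | Emergent, % | Ratio | Difference in both, points | Half-width, any / emergent |
|---|---|---|---|---|---|---|
| 0% | 5.0 vs 15.0 | 3.00 | 5.0 vs 15.0 | 3.00 | 10.0 | 9.8 / 9.8 |
| 5% | 9.75 vs 19.25 | 1.97 | 4.75 vs 14.25 | 3.00 | 9.5 | 11.6 / 9.6 |
| 10% | 14.5 vs 23.5 | 1.62 | 4.5 vs 13.5 | 3.00 | 9.0 | 12.9 / 9.4 |
| 30% | 33.5 vs 40.5 | 1.21 | 3.5 vs 10.5 | 3.00 | 7.0 | 16.0 / 8.4 |

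If only half of the baseline grades persist (q = 0.5, b = 10%), the any-grade ratio is 1.95.

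The term b·q is the same in both groups and cancels from the difference, so the two tables show the same absolute difference in expectation. It falls as b rises only because fewer participants remain at risk. What suffers in the highest-grade table is the ratio and the precision.

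**The case against.** The strongest reply is that SAP 8.2 already shows changes from baseline in several ways, that Protocol 10.6.2 itself specifies incidence by highest grade without a worsening condition, and that "No hypothesis testing is planned for any of the safety endpoints". With a single scheduled post-baseline sample, anyone can read the new-or-worsened counts off the Day 51 shift table. This stands for scheduled samples.

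There is also a second route. Protocol 8.3.2 and 9.2.3 require confirmed Grade 3 or higher results, and any change judged clinically significant, to be recorded as adverse events, where the new-or-worsened rule applies. That narrows the gap to lesser worsening seen only at an unscheduled or early-withdrawal draw. It does not close it.

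Three further limits are fair. The issue is small for the six chemistry tests barred above the upper limit at screening. It does not arise for the hemoglobin-decrease rows of Protocol Table 13, which are graded against baseline. And SAP 8.2 treats in-range values as Grade 0, so a baseline grade needs an out-of-range value that also meets a Table 13 threshold.

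A reader might infer that true falls in neutrophils or lymphocytes would be lost. The documents do not support that: the shift tables and changes from baseline would show them at Day 51. Protocol 2.3.2.2 describes those falls as transient, so the timing of the scheduled sample, four weeks after the second vaccination, limits their detection more than this table does.

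**Conclusion.** The point holds as a gap in definition and display. Read as written, the graded incidence figure counts unchanged pre-existing grades together with new ones; this rests on the SAP's silence about baseline, not on an explicit instruction. The shift table separates them for scheduled Day 51 samples only. No planned laboratory summary both refers to baseline and covers the worst post-baseline result.

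The consequence is confined to how a descriptive endpoint is interpreted and how precise it is. No test or study conclusion depends on it. Its size cannot be computed from the documents; the ratios above depend entirely on the assumed baseline rates, persistence and onset rates.

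Two stronger inferences should be resisted. One is that a true excess under co-administration is hidden: the choice of table does not change the expected absolute difference. The other is that the Grade 3 or higher summary should be restricted to worsened results: Protocol 10.6.2 calls for all such results to be listed, and dropping some would reduce what a safety reader can see.

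**What to change.** In SAP 8.2:

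1. Define a treatment-emergent laboratory abnormality as a post-baseline grade above the baseline grade, using the baseline of SAP 3.5.
2. Add one table of baseline grade (0 to 4) by worst post-baseline grade, by analyte and treatment group, including unscheduled and early-withdrawal results. Show participants without a baseline result in a separate row.
3. Keep the existing highest-grade table, relabelled as any post-baseline grade.
4. Keep every Grade 3 or higher result in its summary and flag those worsened from baseline.

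The cost is one definition, one table and one flag. The central laboratory already assigns the grades, so no new data are needed, and no clinical procedure changes.
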